7.1 DEMOGRAPHIC AND OTHER BASELINE CHARACTERISTICS

Only descriptive statistics are planned for this section of the CTR.

7.2 CONCOMITANT DISEASES AND MEDICATION

Concomitant diseases will be coded according to the most recent version of MedDRA. Concomitant medication will be coded according to the most recent version of the World Health Organisation – Drug Dictionary. Concomitant non-drug therapies will be coded according to the most recent version of MedDRA.

A medication will be considered concomitant, if it

- is ongoing at the time of first study drug administration, or
- starts within the analysis phase of the respective treatment (see [Section 6.1](#) for a definition of treatments and analysis phases).

The relevance of the concomitant therapies to the evaluation of PK will be decided no later than at the RPM.

Only descriptive statistics are planned for this section of the CTR.

7.3 TREATMENT COMPLIANCE

Treatment compliance will not be analyzed as a specific endpoint. Any deviations from complete intake will be addressed in the Report Planning Meeting (cf. [Section 6.2](#)) and described in the CTR.

7.4 PRIMARY ENDPOINTS

7.4.1 Primary analysis of the primary endpoints

Primary analysis of the primary endpoints will be performed as defined in Sections 7.3.1 of the CTP.

The statistical model for the primary analysis defined in the CTP is an analysis of variance (ANOVA) model on the logarithmic scale including "treatment" as fixed effects and "subject" as random effect. Relative bioavailability of the study treatments will be estimated by the ratios of the geometric means

- treatment B (Test 1)/treatment A (Reference 1) (part 1)
- treatment D (Test 2)/treatment C (Reference 2) (part 2)

of the primary endpoints.

Exclusion of PK parameters

The ADS ADPP contains column variables APEXC and APEXCO indicating inclusion/exclusion (APEXC) of a PK parameter and an analysis flag comment (APEXCO). All analyses based on the PKs are based on PK parameter values which are not flagged for exclusion, i.e. with APEXC equal to "Included".

Exclusion of plasma concentrations

The ADS ADPC (PK concentrations per time-point or per time-interval) contains column variables ACEXC or ACEXCO indicating inclusion/exclusion (ACEXC) of a concentration and an analysis flag comment (ACEXCO). Exclusion of a concentration depends on the analysis flag comment ACEXCO. For example, if ACEXCO is set to "ALL CALC", the value will be excluded for all types of analyses based on concentrations. If ACEXCO is set to "DESC STATS" the value will be excluded from descriptive evaluations per planned time point/time interval. If ACEXCO contains the addition "TIME VIOLATION" or "TIME DEVIATION", the value can be used for further analyses based on actual times. If ACEXCO is set to "HALF LIFE", the value will be excluded from half-life calculation only; the value is included for all other analyses. Excluded concentration itself will be listed in the CTR associated with an appropriate flag.

Further details are given in "Noncompartmental Pharmacokinetic / Pharmacodynamic Analyses of Clinical Studies" (4) and "Description of Analytical Transfer Files and PK/PD Data Files" (5).

7.5 SECONDARY ENDPOINTS

7.5.1 Key secondary endpoints

This section is not applicable as no key secondary endpoint has been specified in the protocol.

7.5.2 Secondary endpoints

The secondary endpoints will be statistically analysed in the same way as for the primary endpoints. The endpoints will also be assessed descriptively. The analysis of standard PK parameters is performed according to BI standards (4).

See [Section 7.4](#) of this TSAP for details regarding exclusion of PK parameters and plasma concentrations.

7.6.2 Safety parameters

Safety endpoints and tolerability will be analysed as described in [Section 7.8](#) of this TSAP.

7.7 EXTENT OF EXPOSURE

Descriptive statistics are planned for this section of the report.

7.8 SAFETY ANALYSIS

All safety analyses will be performed on the TS.

7.8.1 Adverse Events

AEs will be coded with the most recent version of MedDRA.

The analyses of AEs will be descriptive in nature. All analyses of AEs will be based on the number of subjects with AEs and not on the number of AEs.

For analysis, multiple AE occurrence data on the eCRF will be collapsed into one event provided that all of the following applies:

- All AE attributes are identical (lower level term, intensity, action taken, therapy required, seriousness, reason for seriousness, relationship, outcome, AESI)
- The occurrences were time-overlapping or time-adjacent (time-adjacency of two occurrences is given if the second occurrence started at most 1 hour after the first occurrence ended)

For further details on summarization of AE data, please refer to "Analysis and Presentation of Adverse Event Data from Clinical Trials" ([7](#)) and "Handling of missing and incomplete AE dates" ([3](#)).

The analysis of AEs will be based on the concept of treatment emergent AEs. That means that all AEs will be assigned to screening, on-treatment or follow-up phases as defined in [Section 6.1](#). AEs will be analysed based on actual treatments, as defined in [Table 6.1: 3](#) and [Table 6.1: 4](#).

An overall summary of AEs will be presented. This overall summary will comprise summary statistics for the class of other significant AEs according to ICH E3 ([8](#)) and for the class of AESIs.

CTP: *The following are considered as AESIs:*

- *Hepatic injury*
A hepatic injury is defined by the following alterations of hepatic laboratory parameters:
 - *An elevation of AST (aspartate transaminase) and/or ALT (alanine transaminase) ≥ 3 -fold ULN combined with an elevation of total bilirubin ≥ 2 -fold ULN measured in the same blood sample, or*
 - *Aminotransferase (ALT, and/or AST) elevations ≥ 10 fold ULN*

The investigator had to classify on the eCRF whether an observed AE was an AESI or not.

According to ICH E3 (8) AEs classified as "other significant" need to be reported and will include those non-serious and non-significant AEs

- (i) which are marked haematological or other lab abnormalities, or
- (ii) which were reported with "action taken = discontinuation" or "action taken = reduced", or
- (iii) which lead to significant concomitant therapy as identified by the Clinical Monitor/Investigator at a Medical Quality Review Meeting.

The frequency of subjects with AEs will be summarised by treatment, primary SOC and preferred term. AEs which were considered by the investigator to be drug related will be summarised separately. Separate tables will also be provided for subjects with SAEs, subjects with AESIs and subjects with other significant AEs (according to ICH E3 (8)). AEs will also be summarized by maximum intensity.

The SOC and preferred terms within SOC will be sorted by descending frequency over all treatment groups.

For disclosure of AE data on ClinicalTrials.gov, the frequency of subjects with non-serious AEs occurring with an incidence of greater than 5 % (in preferred terms) will be summarised by treatment, primary SOC and preferred term. The frequency of subjects with SAEs will also be summarised.

For disclosure of AE data in the EudraCT register, the frequency of AEs, the frequency of non-serious AEs with an incidence of greater than 5 % (in preferred terms) and the frequency of SAEs will be summarized.

For support of lay summaries, the frequency of subjects with drug-related SAEs will be summarized by treatment, primary SOC and preferred term.

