No subject was withdrawn from the study for safety reasons. There were no deaths or serious adverse events reported. All of the observed AEs were considered to be resolved. Given this information, the study drugs appeared to be well-tolerated and there were no safety concerns observed [[R15-4356](#)].
- A study to investigate the pharmacokinetic drug-drug interaction following oral administration of BI 409306 and donepezil in 32 healthy male (n = 17) and female (n = 15) subjects. Part 1 of this trial was performed as a one fixed sequence, open-label trial, in which single doses of BI 409306 and multiple doses of donepezil (5 mg qd for 7 days followed by 10 mg qd for 14 days) were administered, Part 2 of this trial was a randomised, open-label, 2-way crossover design, in which single doses of donepezil and multiple doses of BI 409306 were given.
In Part 1 of the trial, i.e. after multiple doses of donepezil, 16 out of 18 subjects (88.9%) were reported with at least 1 AE that was assessed as drug-related. The most frequently reported drug-related AEs were dizziness and nausea (both 55.6% of subjects), followed by headache and fatigue (both 22.2%). Dizziness was only observed after administration of donepezil alone, whereas nausea and headache were observed after administration of donepezil alone and in combination with BI 409306. As expected visual brightness a known AE of BI 409306 was only observed after BI 409306 administration. Fatigue was observed in all 3 treatment phases.
All subjects completed the trial except for 1 subject in Part 1 who withdrew during the second treatment period (donepezil administration) because of AEs that were considered not to be drug-related (lower abdominal pain, haematochezia, and ruptured ovarian cyst) [[c09564954](#)].

According to [[R15-4794](#), [R18-3913](#)], the safety profile mainly results from the cholinergic activity of donepezil, resulting in

- Gastrointestinal symptoms (e.g. nausea, diarrhea, vomiting, abdominal pain, gastric and duodenal ulcers and gastrointestinal hemorrhage)
- Cardiac symptoms (e.g. syncope, bradycardia, sino-atrial block, atrioventricular block)
- Central-nervous symptoms (e.g. syncope, dizziness, insomnia, seizures, extrapyramidal symptoms and neuroleptic malignant syndrome)

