7.3.4 Safety analyses

Safety will be analysed based on the assessments described in [Section 2.2.2.2](#). All treated subjects (TS, refer to [Section 7.2](#)) will be included in the safety analysis. Safety analyses will be descriptive in nature and based on BI standards. No hypothesis testing is planned.

For all analyses, the treatment actually administered (= treatment at onset) to the subject will be used (any deviations from the randomised treatment will be discussed in the minutes of the Report Planning Meeting).

Treatments will be compared in a descriptive way. Tabulations of frequencies/proportions will be used to evaluate categorical (qualitative) data, and tabulations of descriptive statistics will be used to analyse continuous (quantitative) data.

Measurements (such as vital signs, or laboratory parameters) or AEs will be assigned to treatments (see [Section 4.1](#)) based on the actual treatment at the planned time of the measurement or on the recorded time of AE onset (concept of treatment emergent AEs). Therefore, measurements planned or AEs recorded prior to first intake of trial medication will be assigned to the screening period, those between first trial medication intake and end of REP (see [Section 1.2.3](#)) will be assigned to the treatment period. Events occurring after the REP but prior to next intake or end of trial termination date will be assigned to 'follow-up'. In case of two or more treatments, the follow-up will be summarized according to the previous treatment. These assignments including the corresponding time intervals will be defined in detail in the TSAP. Note that AEs occurring after the last per protocol contact but entered before final database lock will be reported to Pharmacovigilance only and will not be captured in the trial database.

Additionally, further treatment intervals (analysing treatments) may be defined in the TSAP in order to provide summary statistics for time intervals, such as combined treatments, on-treatment totals, or periods without treatment effects (such as screening and follow-up intervals).

Adverse events will be coded using the Medical Dictionary for Regulatory Activities (MedDRA). Frequency, severity, and causal relationship of AEs will be tabulated by treatment, system organ class, and preferred term. SAEs, AESIs (see [Section 5.2.7.1](#)), and other significant AEs (according to ICH E3) will be listed separately.

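### SAP 7.8.1 can merge an AE that ended before the co-administration dose with a matching re-onset up to 1 h later, after the dose, so the re-onset is not counted under the combination

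*SAP*

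**What the plan says.** SAP 7.8.1 says that "multiple AE occurrence data on the eCRF will be collapsed into one event provided that all of the following applies", and gives two conditions. The first is "All AE attributes are identical (lower level term, intensity, action taken, therapy required, seriousness, reason for seriousness, relationship, outcome, AESI"; treatment and analysis phase are not among the nine attributes. The second begins "The occurrences were time-overlapping or time-adjacent", and adjacency is defined as follows: "time-adjacency of two occurrences is given if the second occurrence started at most 1 hour after the first occurrence ended".

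The same section then says that "all AEs will be assigned to screening, on-treatment or follow-up phases as defined in" Section 6.1. Protocol 7.3.4 gives the assignment key: AEs go to treatments "based on the actual treatment at the planned time of the measurement or on the recorded time of AE onset".

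In SAP Tables 6.1: 3 and 6.1: 4 the combination phases open at dosing times. In Part 1 these are the first donepezil dose (BI 425809 still within its residual effect period, REP) and the second BI 425809 dose. In Part 2 it is the second donepezil dose. AE tables count subjects with events, not events.

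**The concern.** The point of the phase structure is to show which AEs begin on one drug alone and which begin on both. The merging rule can undo this at the moment that matters most, the co-administration dose. If a symptom has resolved, the subject takes the combination, and the same symptom starts again within an hour of its earlier end, the second onset is a post-dose onset. Under the rule as written it ceases to be an event of its own.

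The single-drug column keeps its event and the combination column loses one. In Part 1, at the Day 22 dose, the subject can also drop out of *Total BI part 1*, because that total covers only phases involving BI 425809 and *Don part 1* is not one of them. With 18 and 14 subjects, a single case can decide whether a term appears in the combination column at all.

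**Working it through.** The plan gives no figure for merged events. The nearest stated figures are the planned phase durations in SAP 6.1, which fix the boundaries, so these are reproduced first.

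**Inputs.** REP 11 days for BI 425809 and 15 days for donepezil (protocol 1.2.3); dosing days from the Flow Chart and protocol 4.1.4; 18 and 14 subjects (protocol 7.7).

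**Phase durations, Part 1** (day 0 = first BI 425809 dose). First donepezil dose: day 8. Second BI 425809 dose: 8 + 21 = day 29. Last donepezil dose: 8 + 27 = day 35.
- BI: 8 − 0 = 8 days.
- Don + BI: (11 − 8) + 11 = 14 days.
- Don: (29 − 11) + [(35 + 15) − (29 + 11)] = 18 + 10 = 28 days.

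**Phase durations, Part 2** (day 0 = first donepezil dose). First BI 425809 dose: day 15. Second donepezil dose: 15 + 9 = day 24. Last BI 425809 dose: 15 + 23 = day 38.
- Don: 15 days.
- BI: (24 − 15) + [(38 + 11) − (24 + 15)] = 9 + 10 = 19 days.
- BI + Don: 15 days.

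All six agree with the SAP (8, 28, 14 and 15, 19, 15).

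**Boundaries that involve a combination phase**

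| Part | Day | Set by | Change | Merging at the earlier onset removes the event from |
|---|---|---|---|---|
| 1 | 8 | first donepezil dose | BI to Don + BI | combination |
| 1 | 11 | REP end | Don + BI to Don | single drug |
| 1 | 29 | second BI 425809 dose (Visit 3 Day 22) | Don to Don + BI | combination |
| 1 | 40 | REP end | Don + BI to Don | single drug |
| 2 | 24 | second donepezil dose (Visit 3 Day 10) | BI to BI + Don | combination |
| 2 | 39 | REP end | BI + Don to BI | single drug |

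**Hypothetical example at the Part 1 Day 22 dose** (18:00 = hour 0), all nine attributes identical. Record 1 runs from −3 h to −0.25 h; record 2 starts at +0.5 h.
- Gap = 0.5 − (−0.25) = 0.75 h, which is at most 1 h, so the records merge.
- As written, with the earlier onset kept: onset −3 h, counted under *Don part 1* only.
- Kept separate: onsets −3 h and +0.5 h, counted under *Don part 1* and *Don + BI part 1*.

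**How narrow the window is.** For a gap of at most 1 h to span the dose, record 1 must end within the hour before it and record 2 must start within the hour after it.

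**Size per affected subject.** Part 1: 1/18 = 5.6 points. Part 2: 1/14 = 7.1 points. This assumes all planned subjects are in the denominator and the subject has no other AE that counts in the same row of the combination column.

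**The case against.** **The merged onset is not stated.** Neither document says that a merged event takes the first onset, or whether merging precedes phase assignment. A second eCRF record has its own recorded onset, and SAP 4 says the analyses accord with the protocol. SAP 7.8.1 also refers to an internal AE standard, and SAP 6.1 to an ADS plan, neither of which is available here. All of this stands. The earlier onset is the natural reading of collapsing records into one event and then assigning by onset, but it is an inference. The list in 7.8.1 nevertheless reads as complete, and if a restriction exists elsewhere the SAP should state it.

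**Overlapping records.** A reader might extend the criticism to identical records that overlap. If the first entry is still open at the dose, the symptom was already present, and one continuing event at its first onset fits the treatment-emergent concept. Merging there is defensible.

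**Direction.** A reader might infer that fixed sequences make this a one-directional bias against detecting AEs on the combination. The tables do not support that. Phases alternate, and at the three REP-end boundaries listed above the effect runs the other way. Only at the doses that open a combination phase can it do nothing but lower the combination count.

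**Rarity.** A changed intensity, relationship, therapy or action taken blocks the merge, so a worsening after the dose stays visible. Safety is descriptive, the primary endpoints are pharmacokinetic, and individual values are listed. This also stands and limits the weight of the point.

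**Conclusion.** The gap is real but narrow. As written, the rule permits a resolved AE and its matching re-onset within 1 h to be joined across a dose that opens a new phase. With the earlier onset kept, the re-onset is attributed to the phase before that dose. Each affected subject costs the combination column 5.6 points (Part 1) or 7.1 points (Part 2), unless another qualifying AE counts there.

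The number affected is unknown and probably very small, possibly none. The protocol's account of an earlier donepezil interaction trial might suggest otherwise: "The most frequently reported drug-related AEs were dizziness and nausea (both 55.6% of subjects"), that is 10 of 18. That is incidence per subject over multiple dosing, with a different partner compound. It says nothing about matched pairs on either side of one dosing time, and dizziness there was seen only on donepezil alone. No expected frequency can be drawn from it.

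The conclusion rests on two assumptions: that a merged event keeps the earlier onset, and that no unseen standard already bars merging across phases. This is a cheap improvement to a descriptive analysis and does not touch the primary results.

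**What to change.** Add to SAP 7.8.1: time-adjacent occurrences are collapsed only if no new analysis phase of Table 6.1: 3 or 6.1: 4 (including the second part of a two-part phase) began between the end of the first and the start of the second; otherwise they remain separate events, each assigned by its own recorded onset. State also that overlapping identical records remain one continuing event, assigned at the first onset. The condition applies equally at dosing and REP-end boundaries.

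The cost is a sentence or two in the SAP and one condition in the AE dataset program. The downside is that a briefly interrupted episode straddling a boundary counts once in each phase. *Total on-trt* does not change for boundaries between on-treatment phases, because it counts subjects.

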7.8.2 Laboratory data

The analyses of laboratory data will be descriptive in nature and will be based on BI standards "Display and Analysis of Laboratory Data" (9).

Analyses will be based on normalised values, which means transforming to a standard unit and a standard reference range. The original values will be analysed if the transformation into standard unit is not possible for a parameter.

Descriptive statistics of absolute values and change from baseline from laboratory parameters over time (see [Section 6.7](#)) will be provided. Frequency tables of changes between baseline and last value on treatment with respect to the reference range will be presented.

Unscheduled measurements of laboratory data will be assumed to be repeat measurements of the most recent scheduled measurement (e.g. for follow-up or confirmation of a particular value). Therefore, unscheduled measurements will be assigned to the planned time point of the previous scheduled measurement. Descriptive statistics will be calculated by planned time point based on the worst value of the subject at that planned time point (or assigned to that planned time point).

Possibly clinically significant abnormal laboratory values are only those identified either in the Investigator's comments or at the RPM at the latest. It is the Investigator's responsibility to decide whether a lab value is clinically significant abnormal or not. Standard or project-

specific rules for flagging clinically significant values in an automated manner will not be applied in this study.

Clinically relevant findings in laboratory data will be reported as baseline conditions (prior to first administration of study treatment) or as AEs (after first administration of study treatment) if judged clinically relevant by the investigator, and will be analyzed as such.

Results from the fecal occult blood testing will be listed only.

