Regarding donepezil, no inhibition of the metabolism of drugs metabolized by CYP-450 isoenzymes is expected at therapeutic doses of donepezil ([Section 1.2.2](#)).

In summary, a clinically relevant pharmacokinetic interaction causing elevated exposures of donepezil or BI 425809 is considered unlikely.

Safety measures

- Close monitoring of
 - Adverse events
 - Safety lab (special focus on hepatic parameters, markers of GI bleeding (CRP, haematology, iFOB), CK)
 - ECG (focus on possible vagotonic action of donepezil)
 - Vital signs
- Prohibition to use drugs as concomitant therapy that are known to also trigger gastrointestinal ulcers/hemorrhage, e.g. NSAIDs ([Section 4.2.2](#))
- Availability of rescue medication (atropine) in case of signs and symptoms of cholinergic crisis (see [Section 4.2.1](#)).
- Subjects will receive a trial specific emergency card with information for anesthesiologists about the donepezil intake in case of unplanned surgery and potential use of succinylcholine
- As donepezil may impact the ability to operate vehicles and/or machines, subjects participating in Part 1 of this trial subjects are not allowed to drive a vehicle or operate machines during Visit 3
- Although only healthy subjects are allowed to enter this trial per se the investigator has to specifically ask subject's for any life-time history of asthma or seizure resulting in exclusion of the subject

Although rare, a potential for drug-induced liver injury is under constant surveillance by sponsors and regulators. Therefore, this study requires timely detection, evaluation, and follow-up of alterations in selected liver laboratory parameters to ensure subjects' safety.

Overall assessment

Considering the good safety profile of BI 425809 observed so far in healthy subjects, and the safety and tolerability of donepezil up to single doses of 23 mg in healthy volunteers, the unlikelihood of increased drug exposures due to a donepezil-BI 425809 interaction and taking into account the safety measures described in this chapter, the benefit of a successful clinical development of BI 425809 for the treatment of Alzheimer's disease or CIAS is assessed to outweigh the potential risks to healthy subjects participating in this trial that are further considered to be low and acceptable.

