Previous and concomitant therapies will be presented per treatment group without consideration of time intervals and treatment periods.

Laboratory data will be compared to their reference ranges. Values outside the reference range as well as values defined as possibly clinically significant will be highlighted in the listings. Additionally, differences from baseline will be evaluated.

Vital signs or other safety-relevant data will be assessed with regard to possible on-treatment changes from baseline.

Relevant ECG and neurologic findings will be reported as AEs. Fecal occult blood testing results will be listed only.

Suicidality monitoring will be assessed by the C-SSRS questionnaire ([Section 5.2.4](#)). Results will be documented by means of an overall question (“Based on the C-SSRS, has the subject expressed any current suicide ideation or current/past suicide behaviour?” – yes/no) In case this overall question is answered with “yes”, the full questionnaire will be included in the clinical trial report. Findings will be reported as AEs, the completed forms will be stored at the site.

Details for the evaluation of visual tests will be described in the TSAP.

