6. GENERAL ANALYSIS DEFINITIONS

6.1 TREATMENTS

For basic study information on treatments to be administered, assignment of treatment groups, and selection of doses, cf. Section 4 of the CTP.

Each subject is planned to be treated in two subsequent treatment periods in a fixed sequence order. There will be no washout-period between the two treatment periods.

Part 1:

All subjects will receive a single dose of BI 425809 alone in Visit 2 and a single dose of BI 425809 after multiple dosing of donepezil in Visit 3.

Table 6.1: 1 Dosage and treatment schedule part 1

Treatment	Substance	Formulation	Unit strength	Dosage	Total dose
A (Reference 1)	BI 425809	Tablet	25 mg	1 tablet (Day 1, Visit 2)	25 mg
B (Test 1)	Donepezil	Tablet	5 mg	1 tablet (Day 1-7, Visit 3) q.d. 2 tablets (Day 8-28, Visit 3) q.d.	245 mg
	BI 425809	Tablet	25 mg	1 tablet (Day 22, Visit 3)	25 mg

Part 2:

All subjects will receive a single dose of donepezil alone in Visit 2 and then a single dose of donepezil after multiple dosing of BI 425809 in Visit 3.

Table 6.1: 2 Dosage and treatment schedule part 2

Treatment	Substance	Formulation	Unit strength	Dosage	Total dose
C (Reference 2)	Donepezil	Tablet	5 mg	2 tablets (Day 1, Visit 2)	10 mg
D (Test 2)	BI 425809	Tablet	25 mg	1 tablet (Day 1-24, Visit 3) q.d.	600 mg
	Donepezil	Tablet	5 mg	2 tablets (Day 10, Visit 3)	10 mg

For statistical analyses of AEs, vital signs, safety laboratory data and visual tests the following separate analysis phases will be defined for each subject:

Table 6.1: 3 Analysis phases for statistical analysis of AEs, vital signs, safety laboratory data and visual tests, part 1

Study analysis phase	Label	Start	End
Screening	Screening part 1	Date of informed consent	Date/time of first administration of BI 425809
On treatment BI 425809	BI part 1	Date/time of first administration of BI 425809	Date/time of first administration of donepezil
On treatment donepezil	Don part 1	Combination of two phases: First phase: Date/time of first administration of BI 425809 + 11*24h (i.e. REP of BI425809 of 11 days) Second phase: Date/time of second administration of BI 425809 + 11*24h (i.e. REP of BI425809 of 11 days)	Combination of two phases: First phase: Date/time of second administration of BI 425809 Second phase: Date/time of last administration of donepezil + 15*24h (i.e. REP of donepezil of 15 days) or 00:00 a.m. on day after subject's trial termination date whatever occurs earlier

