7. PLANNED ANALYSIS

The format of the listings and tables will follow the BI guideline "Reporting of clinical trials and project summaries" (6).

The individual values of all subjects will be listed. Listings will be sorted by treatment group subject number and visit (if visit is applicable in the respective listing). AE listings will be sorted by assigned treatment (see [Section 7.8.1](#) below for details). The listings will be contained in Appendix 16.2 (SDL) of the CTR.

The following standard descriptive statistical parameters will be displayed in summary tables of continuous variables:

N	number of non-missing observations
Mean	arithmetic mean
SD	standard deviation
Min	minimum
Median	median
Max	maximum

For plasma concentrations as well as for all PK parameters the following descriptive statistics will additionally be calculated:

CV	arithmetic coefficient of variation
gMean	geometric mean
gCV	geometric coefficient of variation

For PK parameters the following descriptive statistics will additionally be calculated:

P10	10 th percentile
Q1	1 st quartile
Q3	3 rd quartile
P90	90 th percentile

The data format for descriptive statistics of plasma concentrations will be identical with the data format of the respective concentrations. The descriptive statistics of PK parameters will be calculated using the individual values with the number of decimal places as provided by the evaluation program. Then the individual values as well as the descriptive statistics will be reported with three significant digits in the CTR.

Tabulations of frequencies for categorical data will include all possible categories and will display the number of observations in a category as well as the percentage (%) relative to the respective treatment group. Percentages will be rounded to one decimal place. The category missing will be displayed if and only if there actually are missing values. Percentages will be based on all subjects in the respective subject set whether they have non-missing values or not.

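### The only frequency table of laboratory values in the SAP uses the last on-treatment value, so no judgement-free count is specified of subjects out of range at any time on treatment

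*SAP*

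**What the plan says.** SAP 7.8.2 plans two kinds of summary for laboratory values.

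- **Shift by reference range.** "Frequency tables of changes between baseline and last value on treatment with respect to the reference range will be presented".
- **Continuous summaries over time**, of absolute values and changes from baseline. "Descriptive statistics will be calculated by planned time point based on the worst value of the subject at that planned time point", with unscheduled draws assigned to the preceding planned time point. SAP 7 lists the statistics printed for continuous variables, including minimum and maximum.

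The handling of individual abnormal values is set out separately:

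- Automated flagging is ruled out. "Possibly clinically significant abnormal laboratory values are only those identified either in the Investigator's comments or at the RPM at the latest".
- Protocol 7.3.4 adds: "Values outside the reference range as well as values defined as possibly clinically significant will be highlighted in the listings".
- "Clinically relevant findings in laboratory data will be reported as baseline conditions (prior to first administration of study treatment) or as AEs", the latter after first dosing and if the investigator judges them clinically relevant.

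SAP 6.1 sets out the treatment phases: "For statistical analyses of AEs, vital signs, safety laboratory data and visual tests the following separate analysis phases will be defined for each subject". Protocol 1.4 names the laboratory focus among its safety measures: "Safety lab (special focus on hepatic parameters, markers of GI bleeding (CRP, haematology, iFOB), CK".

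**The concern.** A shift to the last value answers whether a subject was out of range at the end of treatment. The more natural safety question is whether the subject went out of range at any time on that treatment. Where draws are frequent, the two answers can differ. A transaminase or CK rise, or a haemoglobin fall, that has reversed by the final draw is shown as no change.

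The choice also sits oddly within its own section, where the time-point statistics take the worst value but the shift table takes the last. The section does not say which value counts as last when an unscheduled retest follows the final scheduled draw.

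What is at stake is how completely the descriptive safety tables report the parameters that Protocol 1.4 singles out.

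**Working it through.** **Inputs.** Dose and safety-laboratory times come from the two Flow Charts. The residual effect periods are 11 days (264 h) for BI 425809 and 15 days (360 h) for donepezil (Protocol 1.2.3). Phase limits come from SAP Tables 6.1: 3 and 6.1: 4. Draws marked as drug screen, breath test and pregnancy test only are not counted. A completer without unscheduled draws is assumed.

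**Step 1: reproduce the SAP's phase durations.**

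Part 1, in hours from the first BI 425809 dose. Visit 3 starts at 8 × 24 = 192. The second BI 425809 dose is at 192 + 504 = 696, and the last donepezil dose is at 192 + 648 = 840.

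- BI: 0 to 192, which is 8 days.
- Don + BI: 192 to 264, and 696 to 960. (72 + 264)/24 = 14 days.
- Don: 264 to 696, and 960 to 1200. (432 + 240)/24 = 28 days.

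Part 2, in hours from the start of Visit 3. The second donepezil dose is at 216 and the last BI 425809 dose at 552.

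- BI: 0 to 216, and 576 to 816. (216 + 240)/24 = 19 days.
- BI + Don: 216 to 576. 360/24 = 15 days.

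All five agree with the SAP.

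**Step 2: place the draws on the phases.**

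| Phase | Scheduled draws | Number | Last | Cannot enter |
|---|---|---|---|---|
| BI part 1 | Visit 2: 96, 168 h | 2 | 168 h | 1 |
| Don part 1 | Visit 3: 168, 264, 360, 432, 494 h | 5 | 494 h | 4 |
| Don + BI part 1 | Visit 3: 72 (boundary), 576, 672 h | 3 | 672 h | 2 |
| BI part 2 | Visit 3: 96, 192 h | 2 | 192 h | 1 |
| BI + Don part 2 | Visit 3: 240, 336, 456, 576 (boundary) h | 4 | 576 h | 3 |

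Part 1: 1 + 4 + 2 = 7 of 10 draws cannot enter the shift table. Part 2 Visit 3: 1 + 3 = 4 of 6.

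**Step 3: test the count.**

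- *Boundary draws.* If the Part 1 Visit 3 72 h draw goes to Don, the unused draws are 1 + 5 + 1 = 7. If the Part 2 Visit 3 576 h draw goes to BI, they are 2 + 2 = 4. Neither total changes.
- *End-of-trial draw.* Reading its day as a Visit 3 day, the earliest is 192 + 43 × 24 = 1224 h in Part 1, after 1200, and 35 × 24 = 840 h in Part 2, after 816. Both fall in follow-up.
- *Per subject instead of per phase.* SAP 7.8.2 says only that the last on-treatment value is used. With one value per subject, 9 of 10 draws in Part 1 and 5 of 6 in Part 2 Visit 3 cannot enter.
- *Part 2 Visit 2.* The laboratory column cannot be read reliably in the available text, so those draws are not counted. Six is therefore not the Part 2 total.

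How often a real excursion would be missed depends on its length. The documents give none, so no probability is offered.

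**Step 4: see what else would count a subject who was out of range earlier.**

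- By-time-point minimum and maximum show an extreme at one draw. They do not give the number of subjects out of range, and cannot be combined across draws into such a number.
- Listings mark every out-of-range value but give no count.
- AE tables count subjects, but only for findings judged clinically relevant.
- The hepatic-injury AESI (SAP 7.8.1) needs AST or ALT of at least 3-fold ULN together with bilirubin of at least 2-fold ULN, or AST or ALT of at least 10-fold ULN. CK and haemoglobin have no AESI.
- Other significant AEs include marked laboratory abnormalities and AEs leading to discontinuation, but the finding must first be an AE.

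**The case against.** The strongest reply is that nothing important disappears. A reader might infer from the shift table that transient abnormalities are lost, or that it is the only categorical analysis touching laboratory findings. The documents support neither reading. Every scheduled draw enters the worst-value summaries, every value is listed, and with 18 and 14 subjects the highlighted values can be counted by hand. Clinically relevant findings at any draw reach the AE, AESI and other-significant-AE tables. For the liver the route is wider still. Protocol 3.3.4.1 makes AST or ALT of at least 3-fold ULN, or bilirubin of at least 2-fold ULN, a reason to stop treatment, and an AE with that action falls in the other-significant class. This stands, and it narrows the gap to out-of-range values that are not judged clinically relevant.

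A reader might also infer that the table weakens the close monitoring in Protocol 1.4. It does not: that monitoring is done in real time, and the report format does not change it.

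Two further objections stand in part. The sponsor standard cited in SAP 7.8.2 and the ADS Plan named in SAP 6.1 are not available and may prescribe more tables. And worst-value tables count chance excursions. If each draw had an independent chance p of being out of range (an assumption), the rate over k draws would be 1 − (1 − p)^k. For the Part 1 phases with 2, 5 and 3 draws this gives:

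| p | 2 draws (BI) | 5 draws (Don) | 3 draws (Don + BI) |
|---|---|---|---|
| 2.5% | 5% | 12% | 7% |
| 5% | 10% | 23% | 14% |
| 10% | 19% | 41% | 27% |

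The donepezil phase would look worst with no drug effect at all. That is a reason to print draw counts and keep both tables. It is not a reason to leave the any-time count out.

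**Conclusion.** The point holds in a limited form. The one frequency table of laboratory values named in the SAP uses the last on-treatment value and so omits most scheduled draws: 7 of 10 in Part 1 and 4 of 6 in Part 2 Visit 3. These counts rest on reading the table per SAP 6.1 phase and on the Flow Chart as extracted; assigning the two boundary draws either way leaves them unchanged.

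What is missing is a judgement-free count of subjects who left the reference range at any time on each treatment. Examples are an isolated transaminase rise below the thresholds above, or a CK or haemoglobin change, that the investigator did not consider relevant.

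This is a gap in descriptive safety reporting in an exploratory trial without safety hypothesis tests. It does not affect the pharmacokinetic results, and it does not mean that abnormal values go unseen or unreported. The absence is established only against the protocol and SAP text.

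**What to change.** In SAP 7.8.2:

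1. Add a shift table from baseline to each subject's worst on-treatment value per SAP 6.1 phase, unscheduled draws included. Use the highest value for AST, ALT, GGT, AP, bilirubin, CK, CRP and creatinine; the lowest for haemoglobin, haematocrit and platelets; and both directions otherwise.
2. Keep the last-value table. State whether it is per phase or per subject, and which value counts as last when a retest follows the final scheduled draw.
3. State the phase to which a draw exactly on a boundary belongs.
4. Print the number of draws per phase beside the worst-value table, so that chance excursions in phases with more draws can be judged.

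If the sponsor standard already prescribes such a table, a sentence saying so replaces item 1. The data are already collected, so the cost is SAP wording and one further table.
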